8.1.4. Unsolicited adverse events

Unsolicited AEs occurring during the 28-day follow-up period (day of vaccination and 27 subsequent days) after each vaccination will be recorded in the appropriate section of the eCRF.

8.1.5. Clinical laboratory parameters and other abnormal assessments qualifying as adverse events or serious adverse events

In absence of diagnosis, abnormal laboratory findings (e.g. clinical chemistry, hematology, urinalysis) or other abnormal assessments (e.g. physical examination findings) that are judged by the investigator to be clinically significant will be recorded as AE or SAE if they meet the definition of an AE or SAE (refer to Sections [8.1.1](#) and [8.1.2](#)). The grading of laboratory parameters will be based on the Food and Drug Administration (FDA) Guidance for Industry “Toxicity Grading Scale for Healthy Adult and Adolescent Volunteers Enrolled in Preventive Vaccine Clinical Trials” (refer to [APPENDIX C](#)). Clinically significant abnormal laboratory findings or other abnormal assessments that are present at baseline and significantly worsen following the start of the study will also be reported as AEs or SAEs.

In case of clinically significant grade 3 and above abnormal laboratory findings that cannot be reasonably explained (e.g. due to a pre-existing or current medical condition), the investigator will be recommended to recall the subject in a timely manner (preferably within 7 days after investigator’s awareness/assessment of the abnormal findings) for a repeat test to confirm the result.

The investigator will exercise his/her medical and scientific judgement in deciding whether an abnormal laboratory finding or other abnormal assessment is clinically significant.

8.1.6. Adverse events of specific interest

8.1.6.1. Potential immune-mediated diseases

AEs of specific interest for safety monitoring include pIMDs, a subset of AEs that include autoimmune diseases and other inflammatory and/or neurologic disorders of interest which may or may not have an autoimmune etiology. AEs that need to be recorded and reported as pIMDs include those listed in [Table 20](#).

However, the investigator will exercise his/her medical and scientific judgement in deciding whether other diseases have an autoimmune origin (i.e. pathophysiology involving systemic or organ-specific pathogenic autoantibodies) and should also be recorded as a pIMD.

Once a pIMD is diagnosed (serious or non-serious) in a subject, the investigator (or designate) must complete, date and sign the electronic Expedited Adverse Events Report.

Table 20 List of potential immune-mediated diseases

Neuro-inflammatory disorders	Musculoskeletal disorders	Skin disorders

 • Cranial nerve disorders, including paralyses/paresis (e.g. Bell's palsy) • Optic neuritis • Multiple sclerosis • Transverse myelitis • Guillain-Barré syndrome, including Miller Fisher syndrome and other variants • Acute disseminated encephalomyelitis, including site specific variants (e.g. non-infectious encephalitis, encephalomyelitis, myelitis, myeloradiculoneuritis) • Myasthenia gravis, including Lambert-Eaton myasthenic syndrome • Demyelinating peripheral neuropathies, including: 
 – Chronic inflammatory demyelinating polyneuropathy – Multifocal motor neuropathy – Polyneuropathies associated with monoclonal gammopathy • Narcolepsy 	
 • Systemic lupus erythematosus and associated conditions • Systemic sclerosis (systemic sclerosis), including: 
 – Diffuse scleroderma – CREST syndrome • Idiopathic inflammatory myopathies, including: 
 – Dermatomyositis – Polymyositis • Anti-synthetase syndrome • Rheumatoid arthritis and associated conditions, including: 
 – Juvenile idiopathic arthritis – Still's disease • Polymyalgia rheumatica • Spondyloarthropathies, including: 
 – Ankylosing spondylitis – Reactive arthritis (Reiter's syndrome) – Undifferentiated spondyloarthritis – Psoriatic arthritis – Enteropathic arthritis • Relapsing polychondritis • Mixed connective tissue disorder • Gout 	
 • Psoriasis • Vitiligo • Erythema nodosum • Autoimmune bullous skin diseases (including pemphigus, pemphigoid and dermatitis herpetiformis) • Lichen planus • Sweet's syndrome • Localized Scleroderma (Morphea)
Vasculitides	Blood disorders	Others

 • Large vessels vasculitis, including: 
 – Giant cell arteritis (temporal arteritis) – Takayasu's arteritis • Medium sized and/or small vessels vasculitis, including: 
 – Polyarteritis nodosa – Kawasaki's disease – Microscopic polyangiitis – Wegener's granulomatosis (granulomatosis with polyangiitis) – Churg–Strauss syndrome (allergic granulomatous angiitis or eosinophilic granulomatosis with polyangiitis) – Buerger's disease (thromboangiitis obliterans) – Necrotizing vasculitis (cutaneous or systemic) – Anti-neutrophil cytoplasmic antibody (ANCA) positive vasculitis (type unspecified) – Henoch-Schonlein purpura (IgA vasculitis) – Behcet's syndrome – Leukocytoclastic vasculitis. 	
 • Autoimmune hemolytic anemia • Autoimmune thrombocytopenia • Antiphospholipid syndrome • Pernicious anemia • Autoimmune aplastic anemia • Autoimmune neutropenia • Autoimmune pancytopenia 	
 • Autoimmune glomerulonephritis, including: 
 – IgA nephropathy – Glomerulonephritis rapidly progressive – Membranous glomerulonephritis – Membrano-proliferative glomerulonephritis – Mesangio-proliferative glomerulonephritis – Tubulo-intestinal nephritis and uveitis syndrome • Ocular autoimmune diseases, including: 
 – Autoimmune uveitis – Autoimmune retinitis • Autoimmune myocarditis • Sarcoidosis • Stevens-Johnson syndrome • Sjögren's syndrome • Alopecia areata • Idiopathic pulmonary fibrosis • Good pasture syndrome • Raynaud's phenomenon

Liver disorders	Gastrointestinal disorders	Endocrine disorders

 Autoimmune hepatitis Primary biliary cirrhosis Primary sclerosing cholangitis Autoimmune cholangitis 	
 Inflammatory Bowel disease, including: 
 Crohn's disease Ulcerative colitis Microscopic colitis Ulcerative proctitis Celiac disease Autoimmune pancreatitis 	
 Autoimmune thyroiditis (Hashimoto thyroiditis) Grave's or Basedow's disease Diabetes mellitus type I Addison's disease Polyglandular autoimmune syndrome Autoimmune hypophysitis

When there is enough evidence to make any of the above diagnoses, the AE must be reported as a pIMD. Symptoms, signs or conditions which might (or might not) represent the above diagnoses, should be recorded and reported as AEs but not as pIMDs until the final or definitive diagnosis has been determined, and alternative diagnoses have been eliminated or shown to be less likely.

In order to facilitate the documentation of pIMDs in the eCRF, a pIMD standard questionnaire and a list of preferred terms (PTs) and PT codes corresponding to the above diagnoses will be available to investigators at study start.

8.2. Events or outcomes not qualifying as adverse events or serious adverse events

8.2.1. Pregnancy

Female subjects who are pregnant or lactating at the time of vaccination must not receive additional doses of study vaccines/products but may continue other study procedures at the discretion of the investigator.

While pregnancy itself is not considered an AE or SAE, any adverse pregnancy outcome or complication or elective termination of a pregnancy for medical reasons will be recorded and reported as an AE or a SAE.

Note: The pregnancy itself should always be recorded on the electronic pregnancy report.

The following should always be considered as SAE and will be reported as described in Sections 8.4.1 and 8.4.3:

- Spontaneous pregnancy loss, including:
 - Spontaneous abortion, (spontaneous pregnancy loss before/at 22 weeks of gestation).
 - Ectopic and molar pregnancy.
 - Stillbirth (intrauterine death of fetus after 22 weeks of gestation).

Note: the 22 weeks cut-off in gestational age is based on WHO-ICD 10 noted in the EMA Guideline on pregnancy exposure [[EMA](#), 2006]. It is recognized that national regulations might be different.

- Any early neonatal death (i.e. death of a live born infant occurring within the first 7 days of life).
- Any congenital anomaly or birth defect (as per [CDC MACDP](#) guidelines) identified in the offspring of a study subject (either during pregnancy, at birth or later) regardless of whether the fetus is delivered dead or alive. This includes anomalies identified by prenatal ultrasound, amniocentesis or examination of the products of conception after elective or spontaneous abortion.

Furthermore, any SAE occurring as a result of a post-study pregnancy AND considered by the investigator to be reasonably related to the study vaccines/products will be reported to GSK Biologicals as described in Section [8.4.3](#). While the investigator is not obligated to actively seek this information from former study participants, he/she may learn of a pregnancy through spontaneous reporting.

8.3. Detecting and recording adverse events, serious adverse events and pregnancies

8.3.1. Time period for detecting and recording adverse events, serious adverse events and pregnancies

All AEs starting within 28 days following administration of each dose of study vaccines/products (vaccination day and 27 subsequent days) must be recorded into the appropriate section of the eCRF, irrespective of intensity or whether or not they are considered vaccination-related.

All cases of ILI (refer to Section [5.4.2](#) for the ILI definition) starting after Dose 1 administration (Day 1) up to the study conclusion (Month 26) must be recorded into the appropriate sections of the eCRF (specific screen for recording of ILI and AE/SAE screen, as applicable), irrespective of intensity, or whether or not they are considered vaccination-related, or whether or not they are associated with a medically attended visit.

The time period for collecting and recording MAEs/SAEs will begin at the first receipt of study vaccines/products and will end 12 months following administration of the last dose of study vaccines/products for each subject (Day 1 to Month 26). See Section [8.4](#) for instructions on reporting of SAEs.

All AEs/SAEs leading to withdrawal from the study will be collected and recorded from the time of the first receipt of study vaccines/product.

In addition to the above-mentioned reporting requirements and in order to fulfill international reporting obligations, SAEs that are related to study participation (i.e. protocol-mandated procedures, invasive tests, a change from existing therapy) or are related to a concurrent GSK medication/vaccine will be collected and recorded from the time the subject consents to participate in the study until she/he is discharged from the study.

The time period for collecting and recording pregnancies will begin at the first receipt of study vaccines/products and will end 12 months following administration of the last dose of study vaccines/products. See section [8.4](#) for instructions on reporting of pregnancies.

The time period for collecting and recording of pIMDs will begin at the first receipt of study vaccines/products and will end 12 months following administration of the last dose of study vaccines/products. See section [8.4](#) for instructions on reporting of pIMDs.

An overview of the protocol-required reporting periods for AEs, SAEs, MAEs, pIMDs and pregnancies is given in [Table 21](#).

Table 21 Reporting periods for collecting safety information

Event	Screen. Visit*	Visit 1			Visit 4			Visit 8			Study Conclusion Month 26
		Day 1	7 days post-vacc	28 days post-vacc	Day 57	7 days post-vacc	28 days post-vacc	Month 14	7 days post-vacc	28 days post-vacc	
Solicited local and general AEs											
Unsolicited AEs											
ILIs											
AEs/SAEs leading to withdrawal from the study											
SAEs MAEs											
SAEs related to study participation or concurrent GSK medication/vaccine**											
Pregnancies											
pIMDs											

Vacc = vaccination

*Only applicable for Phase I subjects

**To be collected as of consent obtained (e.g. at Screening visit for Phase I subjects and at Visit 1 for Phase II subjects)

Screen. = screening; AEs = adverse events; ILIs = influenza-like illnesses; SAEs = serious adverse events; MAEs = medically attended events; pIMDs = potential immune-mediated diseases

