Record any intercurrent medical conditions		●	●	●	●	●	●	●	●	●	●	●	●	
Distribution of diary cards ¹	0		0	0		0	0	0		0	0	0	0	
Recording of solicited AEs within 7 days post-vaccination		●	●		●	●			●	●				
Recording of unsolicited AEs within 28 days post-vaccination		●	●	●	●	●	●		●	●	●			
Recording of ILIs as unsolicited AEs/SAE, as applicable		●	●	●	●	●	●	●	●	●	●	●	●	
Return of diary cards		0	0	0	0	0	0	0	0	0	0	0	0	
Diary card transcription by investigator		●	●	●	●	●	●	●	●	●	●	●	●	
Recording of AEs and SAEs leading to withdrawal from the study		●	●	●	●	●	●	●	●	●	●	●	●	
Recording of SAEs, MAEs, pIMDs and pregnancies		●	●	●	●	●	●	●	●	●	●	●	●	
Recording of SAEs related to study participation, or to a concurrent GSK medication/vaccine	●	●	●	●	●	●	●	●	●	●	●	●	●	
Screening conclusion	●													
Study conclusion													●	

Note: the double-line border following Day 85 and Month 14 + 28 days indicates the analyses which will be performed on all data (i.e. data that are as clean as possible) obtained up to Day 85 and Month 14 + 28 days, respectively.

D = day; M = month (= 28 days); PRE = pre-vaccination; PI = post-dose 1; PII = post-dose 2; PIII = post-dose 3 (booster)

AE = adverse events, ILI = influenza-like illness; SAE = serious adverse event; MAE = medically attended event; pIMD = potential immune-mediated disease

● is used to indicate a study procedure that requires documentation in the individual eCRF

CONFIDENTIAL

207543 (FLU D-SUV-ADJ-001)
Protocol Amendment 4 Final

○ is used to indicate a study procedure that does not require documentation in the individual eCRF

* Screening evaluations may be completed 2 to 28 days before Day 1. Site staff should allow sufficient time between the Screening and Visit 1 to receive and review screening safety laboratory test results. If a delay occurs such that the interval between Screening and the Visit 1 vaccination exceeds 28 days, a re-screening visit should be scheduled before Visit 1 during which blood sample collection for safety laboratory assessment must be repeated; an interim medical history and physical examination must be obtained and inclusion / exclusion criteria must be re-reviewed. Only data from the re-screening visit, if it occurs, will be recorded in the eCRF and taken into consideration.

** This visit is only applicable following passive surveillance contacts for subjects with ILI (see Section 5.4.2).

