6.5. Contraindications to subsequent vaccination

The following events constitute absolute contraindications to further administration of any study vaccines/products. If any of these events occur during the study, the subject must not receive additional doses of vaccines/products but may continue other study procedures at the discretion of the investigator (see Section 8.5):

- Anaphylaxis following the administration of vaccine(s)/product(s).
- Pregnancy (see Section 8.2.1).
- Any condition that in the judgment of the investigator would make intramuscular injection unsafe.
- Occurrence of an SAE judged to be vaccine-related by the investigator.
- Occurrence of a new pIMD or the exacerbation of an existing pIMD. Refer to Section 8.1.6.1 for the definition of pIMDs.
- Discovery of any health condition which, in the investigator's opinion, places the subject at increased risk from receiving further study vaccines dose(s); or discovery of a change in the subject's health status which make him/her unable to comply with protocol-mandated safety follow-up.
- Hypersensitivity to the active substances or to any of the excipients or to any component that may be present as traces.

The following events constitute contraindications to administration of any study vaccines/products at that point in time; if any of these events occur at the time scheduled for vaccination, the subject may be vaccinated at a later date, within the time window specified in the protocol (see Section 5.5), or the subject may be withdrawn at the discretion of the investigator (see Section 8.5):

- Acute disease and/or fever at the time of vaccination.
 - Fever is defined as temperature $\geq 38.0^{\circ}\text{C} / 100.4^{\circ}\text{F}$. The preferred location for measuring temperature in this study will be the oral cavity.
 - Subjects with a minor illness (such as mild diarrhea, mild upper respiratory infection) without fever can be administered all vaccines/products.

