9.2.2. Subject withdrawal from study vaccines/products

A ‘withdrawal’ from the study vaccines/products refers to any subject who does not receive the complete treatment, i.e. when no further planned dose is administered from the date of withdrawal. A subject withdrawn from the study vaccines/products may not necessarily be withdrawn from the study as further study procedures or follow-up may be performed (safety or immunogenicity) if planned in the study protocol.

Information relative to premature discontinuation of the study vaccines/products will be documented on the Vaccine Administration screen of the eCRF. The investigator will document whether the decision to discontinue further vaccination/treatment was made by the subject himself/herself, or by the investigator, as well as which of the following possible reasons was responsible for withdrawal:

- Serious adverse event.
- Unsolicited non-serious adverse event.
- Solicited adverse event
- Not willing to be vaccinated
- Other (specify).

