10. STATISTICAL METHODS

10.1. Primary endpoints

Reactogenicity and safety

- Occurrence of solicited local and general AEs after each vaccination:
 - Occurrence of solicited local AEs during a 7-day follow-up period (i.e. on the day of vaccination and 6 subsequent days) after each vaccine dose, in all vaccine groups.
 - Occurrence of solicited general AEs during a 7-day follow-up period (i.e. on the day of vaccination and 6 subsequent days) after each vaccine dose, in all vaccine groups.
- Occurrence of unsolicited AEs after each vaccination:
 - Occurrence of unsolicited AEs during a 28-day follow-up period (i.e. on the day of vaccination and 27 subsequent days) after each vaccine dose, in all vaccine groups.
- Occurrence of hematological and biochemical laboratory abnormalities after each vaccination:
 - Any hematological (red blood cells, white blood cells and differential count, platelets count and hemoglobin level) or biochemical (alanine aminotransferase, aspartate aminotransferase, creatinine, blood urea nitrogen [BUN] and BUN-to-creatinine ratio) laboratory abnormality at each visit subsequent to Day 1, in all vaccine groups.
- Occurrence of MAEs, pIMDs and SAEs:
 - Occurrence of MAEs, pIMDs and SAEs throughout the entire study period, in all vaccine groups.

Immunogenicity

Anti-H1 stalk immune response measured by ELISA and by MN assay 28 days after each priming dose:

- Levels of anti-H1 stalk antibody titers by ELISA and by MN assay.

The following aggregate variables will be calculated for the above parameters with 95% confidence interval (CI):

- Seropositivity rates and geometric mean titers (GMTs) at Days 1, 29 and 85.

- Percentage of subjects with a \geq 4-fold increase from Day 1 to Days 29 and 85.
- Percentage of subjects with a \geq 10-fold increase from Day 1 to Days 29 and 85.
- Mean geometric increase (MGI) from Day 1 to Days 29 and 85.

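### Section 8.3.1 ends MAE/SAE, pIMD and pregnancy collection 12 months after the last dose, which contradicts the whole-study safety endpoint and Tables 5 and 6 for subjects who stay in the study but miss the booster

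*Protocol*

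**What the plan says.** Protocol Section 8.3.1 sets the collection windows. For MAEs and SAEs, collection starts at the first dose and "will end 12 months following administration of the last dose of study vaccines/products for each subject (Day 1 to Month 26"). For pIMDs it says: "The time period for collecting and recording of pIMDs will begin at the first receipt of study vaccines/products and will end 12 months following administration"; here too the count starts from the final dose, but Month 26 is not mentioned. The pregnancy sentence has the same form as the pIMD sentence. In the same section, ILI cases are recorded if "starting after Dose 1 administration (Day 1) up to the study conclusion (Month 26"), an end that does not depend on dosing.

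Section 10.1 makes the following a primary endpoint: "Occurrence of MAEs, pIMDs and SAEs throughout the entire study period, in all vaccine groups". In Tables 5 and 6, the row for SAEs, MAEs, pIMDs and pregnancies is marked at every visit from Visit 1 to Visit 12 (Month 26), with no exception for subjects who have stopped vaccination. Section 5.6.16 collects MAEs over the whole study.

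The protocol expects some subjects to stay in the study without further doses. Under Section 6.5, a subject with a contraindication such as a vaccine-related SAE or a new pIMD "must not receive additional doses of vaccines/products but may continue other study procedures at the discretion of the investigator". Section 9.2.2 adds: "A subject withdrawn from the study vaccines/products may not necessarily be withdrawn from the study".

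**The concern.** A window that ends 12 months after the last dose closes at Month 26 only if the last dose was the Month 14 booster. For anyone who stops earlier and remains in the study, Section 8.3.1 points to an earlier end than the primary endpoint and the schedule of procedures. No readable text says which rule governs.

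The MAE/SAE sentence conflicts with itself for these subjects, because its bracket gives Month 26 while its rule gives an earlier date. The pIMD and pregnancy sentences have no bracket, so their literal reading is plainer. The contrast with the ILI sentence can also suggest to a site that the dose-based end was intended.

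Sites could therefore record the same event types over different windows. Section 8.4.1 ties prompt reporting of SAEs, pregnancies and pIMDs to the period defined in Section 8.3, so the ambiguity carries into expedited reporting. For MAEs, Section 10.8 plans a percentage of subjects, and Section 10.6 counts a subject with no reported MAE as having had none; a shortened window could lower that percentage. Section 10.8 describes SAEs and pIMDs in detail, so for them the risk is that cases go unrecorded. Pregnancies are not part of the primary endpoint, but the same contradiction with Tables 5 and 6 applies.

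**Working it through.** **Inputs**
- Optimal intervals, Table 7: Visit 1 to Visit 4, 56 days; Visit 4 to Visit 8, 336 days; Visit 8 to Visit 12, 336 days.
- Latest allowed intervals, Table 7: 66, 364 and 364 days.
- Length of a study month, footnote to Tables 5 and 6: "M = month (= 28 days"). Twelve months are therefore 12 × 28 = 336 days.
- Dosing visits, Section 3 and Table 17: Day 1, Day 57 and Month 14. The Day 57 injection is PBS in some groups; it still counts as a dose, because Section 8.3.1 refers to vaccines/products.

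**Reproducing the protocol's Month 26**
- Booster: 56 + 336 = 392 days after Day 1, and 392 / 28 = Month 14.
- Twelve months later: 392 + 336 = 728 days, and 728 / 28 = Month 26.

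The bracket in the MAE/SAE sentence is thus exactly right for a subject who receives the booster.

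**The same rule without the booster**

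End of window = day of last dose + 336. Days lost = 728 − end of window.

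| Last dose | Window ends | Days lost | Share of 728 days |
|---|---|---|---|
| Day 1 | 0 + 336 = 336 (Month 12) | 392 | 53.8% |
| Day 57 | 56 + 336 = 392 (Month 14) | 336 | 46.2% |

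**Sensitivity**
- Reading 12 months as 365 days (an assumption): the window ends at day 365 or 56 + 365 = 421. The loss is 363 days (49.9%) or 307 days (42.2%).
- Latest allowed visits: the study ends at 66 + 364 + 364 = 794 days. The window ends at day 336 or 66 + 336 = 402. The loss is 458 days (57.7%) or 392 days (49.4%).
- If Month 26 governs for every subject still followed, nothing is lost.

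**Whether other provisions close the gap**
- Section 8.3.1 collects SAEs related to study participation, or to a concurrent sponsor product, until discharge. This does not cover MAEs, pIMDs or other SAEs.
- Section 8.5.1 follows events already documented. It does not require a search for new ones.
- Section 8.3.2 defines post-study events by reference to Table 21. That table's columns end at the Month 26 study conclusion, but the shading that marks the periods cannot be read in the available text.

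**The case against.** The strongest reply is that the protocol already intends collection to Month 26 for everyone. The MAE/SAE sentence says so in its bracket, Tables 5 and 6 make no exception, Section 5.6.16 agrees for MAEs, and the endpoint covers the whole study. Table 21, which Section 8.3.2 treats as defining the reporting period, may say the same. This stands as far as it goes. A reader might infer from Section 8.3.1 that follow-up is definitely cut short in subjects who stop early; the documents do not support that, because several places point to Month 26. The objection does not remove the contradiction, which is clearest for pIMDs and pregnancies, where the sentence has no bracket.

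A reader might also infer that the primary safety rates are biased downward, and more so in the adjuvanted groups. The documents do not establish this:
- Section 10.6 does not name pIMDs in its no-event rule, and the percentage argument applies mainly to MAEs.
- A subject stopped for a related SAE or a new pIMD already counts as having that type of event, so a later one does not change a per-subject occurrence.
- Reasons for stopping vaccination in Section 9.2.2 include unwillingness to be vaccinated, so the affected subjects are not all selected on safety.
- Nothing in the documents links stopping to adjuvant.

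Finally, a reader might conclude that the investigator discretion in Section 6.5 should be narrowed. That discretion is stated consistently in Sections 6.5 and 8.2.1 and contradicts nothing, so it is not part of this point.

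**Conclusion.** The contradiction is real and limited. For subjects who remain in the study but miss the Month 14 booster, Section 8.3.1 read literally ends collection 14 study months early (last dose Day 1) or 12 study months early (last dose Day 57), against a primary endpoint and a visit schedule that run to Month 26. These figures use the optimal visit intervals and the protocol's 28-day month; the alternatives tried give losses of between 42% and 58% of follow-up. They apply only under the literal reading.

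The documents give no number of subjects who stop vaccination yet stay in follow-up. Subjects who leave the study altogether are unaffected, since they have no later data under either rule. The number affected is probably small, and the effect on the endpoint cannot be quantified. The safety analyses are descriptive, so no hypothesis test depends on this. It still merits correction, because a stated rule that sites might follow would shorten ascertainment for a primary safety endpoint.

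**What to change.** Reconcile Section 8.3.1 with Section 10.1 and Tables 5, 6 and 21. In the MAE/SAE, pIMD and pregnancy sentences, replace the end defined by the last dose with one common end: collection runs to Visit 12 (Month 26) or to withdrawal from the study, irrespective of the number of doses received. Check that the periods shaded in Table 21 match. Section 6.5 needs no change.

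The cost is a wording change in one section. The visits and their recording already run to Month 26, so the only added burden is continued recording, at scheduled visits, for the few subjects who stop vaccination but remain in the study.
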